The majority (73.3%) were discharged from the treatment host setting on good terms (with staff approval) and 73.3% did not use substances on or after the onset of PPJ therapy (one person used substances after intake but not again during treatment). Two thirds (66.7%) did not use substances and left on good terms. One used substances and left on good terms. One did not use substances but left against staff advice. Three used substances and left at staff request. Our preliminary work has demonstrated 1) high rates of treatment retention for the "Three Good Things" study, 2) high acceptability and feasibility among AUD patients for the "Three Good Things" exercise and among SUD patients for PPJ, 3) significant impact of the "Three Good Things" exercise on improvement in mood, and 4) revelation of important considerations to address as we implement the intervention moving forward.

- 2.3. Existing Literature: PPJ is a novel intervention, but it draws most strongly from two bodies of research: 1) the research on gratitude and its relationship to addiction recovery (PPJ includes two gratitude exercises on the left hand side of the page) and 2) the research on activity scheduling and behavioral activation to support addiction recovery (featured on PPJ's right hand side page).

Research on Gratitude and Addiction Recovery. Anecdotally we know that gratitude is a strong component of addiction recovery in 12-step programs

such as Alcoholics Anonymous. It is a common theme in AA meetings¹⁸ and is a prevalent theme in AA literature.¹⁹ Recent empirical investigations into this phenomenon suggests that trait gratitude correlates positively with recovery supportive factors and negatively with factors that might challenge recovery.¹⁸ Research also suggests that gratitude practices are associated with improvement in mood, which should make recovery more positively reinforcing.¹⁷ Supporting recovery and improving mood should reduce relapse risk. In the paragraphs that follow, this body of research is described in detail.

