Recurrence of substance use and treatment retention will be assessed via NUWAY treatment record. Research staff will not have direct access to the NUWAY treatment record. A NUWAY staff member will meet with research staff at reasonable intervals to report information about treatment retention and recurrence of substance use for study participants from the NUWAY treatment record (for electronic administration, these meetings will be via Zoom or telephone). Recurrence of substance use is assessed at NUWAY by positive urine analyses (UAs) and other drug screens as well as resident self-report. At or after this meeting, research staff will use the password protected electronic document which links participants' real names with their study codenames/numbers. Research staff will use this key to record the information from NUWAY staff into a de-identified database (e.g. excel or SPSS or Google drive) or into REDCap.

[name], the lead investigator, will keep a log/personal notes throughout the study, qualitatively recording observations, especially during recruitment and after each class session.

A de-identified participant tracker will be maintained on Google drive using only participant codenames to track group attendance, independent practice phase activity and other study activities.

Analysis Plan.

Sample characteristics. We will aggregate information about the demographics and baseline characteristics of the study to be able to describe the psychosocial, demographic, and clinical profile of study participants. We will calculate means and standard deviations for continuous measures (e.g., age) and calculate percentages for categorical measures (e.g., marital status).

Primary feasibility and acceptability measures. We will aggregate information designed to assess feasibility and accessibility such as number of Qualtrics surveys completed, group sessions attended, journal entries completed, as well as participant assessment of the difficulty, ease, helpfulness, satisfaction, and effort expended on PPJ. We will sum these items and calculate means and standard deviations.

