If participants leave NUWAY on good terms during the study period, they may still be able to continue to be in the study because it is possible to continue study activities from outside of NUWAY for the independent practice phase. Any smartphone or tablet can be used to continue to participate in the independent practice phase. We may reach out to participants who continue to participant in this way to encourage them to continue in the study or ask if they wish to remain in the study using the contact information they provide to use through NUWAY Inc.

Follow up Interview: At approximately 30 days after the exit interview, we will follow up with participants. Zoom is the first choice but a telephone interview is acceptable for this procedure. We will ask participants about any substance use and journaling in the past 30 days. We will ask a few additional qualitative questions such as what was most memorable about being in the research study, and other similar questions. Participants will be encouraged to complete their final Qualtrics survey before this interview.

- 5.4. Individually Identifiable Health Information: Research study staff will meet with NUWAY staff at reasonable intervals to collect data on our primary outcomes: 1) treatment retention and 2) recurrence of substance use. At these occasions we will go through our list of study participants and ask NUWAY staff if: 1) that person has left treatment or been asked to leave; 2) that person has had a positive urine analysis screening indicating recurrence of substance use. We will mark down the replies in our deidentified data file. If the participant cannot remember date of entry into NUWAY, we will also gain this information from NUWAY staff and the treatment record. To facilitate this work, study staff will use a password-protected file linking participants' real names with study IDs (codenames/numbers).

6. This study therefore includes PHI and therefore we have combined our informed consent document with the appropriate text from a HIPAA authorization form.

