“in the last week” would mean in the week that ends today. Please know I will not be asking you any follow up questions for any of these next questions. Depending on some of your answers, I might need to let NUWAY staff know of your replies.” We would consider a high score to be two or more past-week symptoms for each subscale: internalizing disorder, externalizing disorder, or criminal/violent behavior. Exclusion from the study based on these items would include endorsing “last week” for certain items such as: “thinking about ending your life or committing suicide,” “lied or conned to get things you wanted or to avoid having to do something,” having a hard time “paying attention at school/work/home” in combination with having a hard time “listening to instructions at school/work/home,” “were a bully or threatened other people,” “started physical fights with other people,” “had a disagreement in which you pushed, grabbed, or shoved someone,” and “purposely damaged or destroyed property that did not belong to you.” In the event of high scores in any of the three subscales or a single score of “last week” for any of these selected items, the person would not be eligible for the study. However, in each of these cases, we would discuss the results with NUWAY staff before determining final eligibility for the study.

8. The requirement of 2 weeks continuous sobriety before enrollment in the study may be waved based on clinical judgment.
9. Participant would read/review/discuss with study staff the informed consent/HIPAA consent combined document. Participant would read/review/discuss with study staff the HIPAA consent document.
10. Research staff would ask the participant the questions from the UBACC quiz to determine capacity to consent.⁵⁷ A score of 15 or higher is needed for inclusion in the study. The prospective participant can review the study details and return to re-do the quiz another day if this is possible given the study timeline.
11. If they score over 15 on the UBACC and meet all other study inclusion/exclusion criteria, or if they are eligible for the wait list, they will sign the main informed consent document (electronically if electronic administration). These forms will be signed in duplicate, providing one copy for research staff and one for participant (duplication unnecessary for electronic administration).
12. If the participant is deemed to meet all study criteria, they would move on to take the baseline assessment instrument.

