20.1. Protecting Privacy: REDCap information will contain the participant's name but all other documents in paper or electronic format will include the person's codename or number only. An electronic file matching participant name to codename or number will be kept on a password protected computers and the file itself will be password protected and erased one year after the conclusion of data analysis. Any paper copies of this information will also be destroyed at this time.

We will go to great lengths to make sure participants understand the nature of the research study and our concern about their privacy. This will be made clear in the content of the informed consent document. We will review this information with participants in depth as we go over all elements of the informed consent process. We will assure the participant that we will do everything we can to ensure their privacy, including using a codename or number associated with their data and putting a password on the electronic file that matches their codename or number to their name. Limitations to confidentiality will also be described, such as whether the participant describes the desire to harm themselves or others, or whether a minor or vulnerable adult is at risk of abuse or neglect. We will ask that participants use a quiet, private room for Zoom meetings and use headphones if at all possible during our Zoom class with them.

20.2. Access to Participants: The research team will not have access to NUWAY records. To determine our key outcomes, recurrence of substance use or discontinuation of treatment, a NUWAY staff member will meet with a member of the research team at reasonable time intervals to share whether participants have left treatment or whether they have resumed

substance use. Resumption of substance use is confirmed at NUWAY via urine testing or other drug screening or client self-report. Results of these tests, if positive for substances, will be communicated to research staff at reasonable periods and we will code this information into our de-identified data records. We will also have staff check the NUWAY record if the individual does not remember the date they started at NUWAY.

21. Compensation for Research-Related Injury

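### Section 5.4 collects recurrence through an undated question about urine screens only, which conflicts with Sections 5.2 and 20.2 and leaves the counting window open

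*Combined protocol and SAP*

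**What the plan says.** Sections 1 and 3.1 list substance use among the primary outcomes, with treatment retention and with feasibility and acceptability. Three sections then describe how recurrence is obtained.

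- **Section 5.4** sets out the collection step: "Research study staff will meet with NUWAY staff at reasonable intervals to collect data on our primary outcomes". Research staff go down the participant list and ask, besides whether the person has left treatment, whether "that person has had a positive urine analysis screening indicating recurrence of substance use. We will mark down the replies in our deidentified data file". The same paragraph allows the date of entry into NUWAY to be taken from the treatment record when the participant cannot recall it.
- **Section 5.2** (text under Outcomes, after Table 2) is wider: "Recurrence of substance use is assessed at NUWAY by positive urine analyses (UAs) and other drug screens as well as resident self-report". It adds that research staff have no direct access to that record.
- **Section 20.2** agrees with 5.2: "Resumption of substance use is confirmed at NUWAY via urine testing or other drug screening or client self-report". It says NUWAY staff share whether participants have resumed use, but its sentence on what is passed on covers tests only: "Results of these tests, if positive for substances, will be communicated to research staff at reasonable periods".

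Table 2 marks recurrence at three points: after Phase 1, after Phase 2, and at final activities including the one-month follow-up. The first two columns are headed as asked or tallied once the phase has ended. There is no baseline mark.

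Separately, the follow-up interview asks both arms about use in the past 30 days (Section 5.3).

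On entry, Section 9.1 requires about two weeks of abstinence and Section 12.1 uses six days at preliminary screening. Section 9.3, item 8 adds: "The requirement of 2 weeks continuous sobriety before enrollment in the study may be waved based on clinical judgment".

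**The concern.** The wording of the question decides what ends up in the data file, and here it is narrower than the outcome definition and has no time frame. Three things follow.

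1. **Source.** A client whose use is known from another kind of screen, or from telling a counsellor, is a recurrence under 5.2 and 20.2. The 5.4 question, taken literally, gets the answer no.
2. **Start point.** Participants are already NUWAY clients when randomised. A positive from earlier in the same treatment episode would satisfy a question that has no start date. Journaling cannot have caused such an event, and if no date is recorded it cannot be separated out later by staff who do not see the record.
3. **Time points.** Table 2 needs status at three points per participant. An undated reply given at a meeting not tied to that participant's phase ends may not show which window the event belongs to.

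If either coding error is equally common in both arms, it pulls the arms together. The observed rates are also meant to feed the sample-size calculation for a larger trial (Section 17.3), so a distorted rate would carry forward.

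**Working it through.** **Step 1. The sections side by side.**

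| | 5.4 (question asked) | 5.2 and 20.2 (definition) | Follow-up interview |
|---|---|---|---|
| Urine test | yes | yes | – |
| Other drug screen | not asked | yes | – |
| Self-report | not asked | yes | yes, past 30 days |
| Event date | not asked | not stated | not stated |
| Start at randomisation | not stated | not stated | not applicable (30-day recall) |
| Timing | unspecified intervals | unspecified intervals | about 30 days after exit interview |

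The interview's 30-day recall starts at about the exit interview, so it does not cover the preceding five weeks. For that period the record is the named source, and 5.4 is the only place that says what is asked of it.

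**Step 2. Can earlier positives arise?** Yes. Section 9.1 requires participants to be current clients, and outpatient treatment generally lasts 90 to 120 days (Section 23.1), so there may be a record that predates randomisation. The abstinence rule limits only the most recent period, and it can be waived. The word recurrence does not exclude a relapse that happened in treatment before randomisation.

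**Step 3. The plan's own power figure.** Inputs from Section 17.2: N=76 (38 per arm, assuming 1:1 allocation), abstinence 41.5% versus 24.8%. With the arcsine method, h = 2·asin(√0.415) − 2·asin(√0.248) and power = Φ(h·√(38/2) − z).

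- One-sided 0.10: 0.609 (stated .61).
- Two-sided 0.05: 0.344 (stated .34).

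Both reproduce. There is no numerical error in the plan on this point.

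**Step 4. Illustration on assumed error rates.** The documents give none, so these are ranges and not estimates. Both errors are taken as equal in the two arms and unrelated to true outcome.

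*(a) A share q is coded recurrent because of an earlier positive.* Abstinence becomes p(1−q). At q=10%: 0.415×0.9 = 0.373 and 0.248×0.9 = 0.223.

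*(b) A share m of true recurrences is missed.* Abstinence becomes 1−(1−p)(1−m). At m=20%: 1−0.585×0.8 = 0.532 and 1−0.752×0.8 = 0.398.

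| Assumption | Power, one-sided 0.10 | Power, two-sided 0.05 |
|---|---|---|
| No error | 0.609 | 0.344 |
| q = 5% | 0.586 | 0.323 |
| q = 10% | 0.564 | 0.302 |
| q = 20% | 0.519 | 0.264 |
| q = 30% | 0.474 | 0.228 |
| m = 10% | 0.525 | 0.269 |
| m = 20% | 0.456 | 0.215 |
| m = 30% | 0.398 | 0.175 |

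With 50 per arm (about 100 in total, Section 11.1), one-sided power is 0.693 without error, 0.645 at q=10% and 0.525 at m=20%.

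**The case against.** The strongest reply is that 5.4 is a health-information section and not the outcome definition. Section 5.2 defines the outcome, 20.2 repeats it, and a sensible team would ask accordingly. The trial's main objective is feasibility and acceptability, and Sections 5.2 and 17.3 say it is not powered to detect effects. At 5% to 10% contamination the loss of one-sided power is only from 0.61 to 0.59 or 0.56. All of this stands and limits the weight of the point. It does not remove the conflict, because 5.4 is where the question itself is written.

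Four stronger readings are tempting, and the documents do not support them.

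- *Positives from before randomisation are counted.* No section says so. The window is unstated, and Table 2 has no baseline mark. Such positives could count; they are not said to.
- *Self-report is excluded from the outcome.* Only the 5.4 question leaves it out. Sections 5.2 and 20.2 include it, and the follow-up interview collects it for its own 30 days.
- *The three Table 2 time points cannot be derived.* The headings call for a tally after each phase, and recruitment is in batches of 10 to 20 (Section 8.1), so cumulative status is available if meetings fall at each phase end. The correct statement is that this is not assured.
- *The development study shows the size of the problem.* Section 2.2 reports that 73.3% of 15 women, that is 11, "did not use substances on or after the onset of PPJ therapy (one person used substances after intake but not again during treatment". The aside may describe one of those 11 or one of the other four. On the second reading an undated count would not change at all. It is one person in any case, at a residential site, and should not be used as a magnitude.

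**Conclusion.** The point holds as an internal conflict with an unstated counting window. Section 5.4 asks about less than 5.2 and 20.2 count, and no section records an event date or starts the count at randomisation. Followed literally, it would under-ascertain recurrence during the five study weeks, could admit earlier positives that cannot be removed afterwards, and does not guarantee status at the three Table 2 points.

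The size is unknown. The power figures rest on assumed error rates, equal in both arms, and on 1:1 allocation; they show only that power which is already low would fall further. Missed recurrences cost more than earlier positives at the same percentage: at 20%, 0.46 against 0.52 (one-sided). This should be corrected, but it does not threaten the feasibility aims.

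**What to change.** Replace the recurrence question in Section 5.4 with wording such as: *Since [randomisation date], has this person had any positive urine or other drug screen, or reported use? Give the date and source of each.*

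Then:

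- count only events dated after randomisation;
- allocate each event by its date to the Table 2 time points, with the phase-end dates written down for each cohort;
- use the same definition in 5.2, 5.4 and 20.2, and correct the sentence in 20.2 that passes on test results only;
- state how the record and the follow-up interview are combined.

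The source field also allows a sensitivity analysis on test results alone. That is useful because Section 10.2 has study staff pass on disclosed use to NUWAY, and the treatment arm spends about eight more hours with study staff.

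The cost is a reworded question, two extra data fields, and slightly more work for NUWAY and research staff at each meeting. No new test or participant contact is needed. Section 5.4 already provides for one date, that of entry, to be taken from the same record.

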The Treatment Group's Group Phase. Participants will meet for 8 hours of group content 2-3 times per week for 3 weeks to learn PPJ. For electronic administration, these groups take place via Zoom.

PI [name] or another trained research staff member will conduct these intervention therapy groups. The primary aim of the groups is to teach the elements of PPJ. Groups and other Zoom meetings will be audio recorded or Zoom's instant audio transcription tool will be used to aid treatment manual development and to collect qualitative data. Zoom meetings will be video recorded (this happens automatically in Zoom), but client images will be edited out so as to completely remove them from the video recordings. These videos will be used by research staff to learn how to lead the treatment groups. The videos will include the audio track and only images of our PowerPoint slides and research study staff images. PPJ is taught by a counselor or group facilitator who themselves uses PPJ on a daily or near daily basis and the facilitator will practice PPJ along with participants in the group setting.

A NUWAY Inc. staff member will sit in on all group sessions. Study staff (research assistants) may also sit in on group sessions and may lead group sessions in the unlikely event of any absence of the primary group leader. [name], primary investigator, would provide supervision and instruction in such an event. NUWAY Inc. staff or research staff will also practice PPJ. Journals will be provided by the study to the study participants. For electronic administration, journals will be mailed or delivered to the participants and to the NUWAY staff member. A set of journals will also be delivered to the NUWAY office as a backup. Clients can pick up a journal on a usual face-to-face visit to NUWAY for drug screening. Journals will have pre-printed category headings listed on the pages (see the figure, above) and other PPJ elements such as note pages, worksheets for describing values and instructions for teaching PPJ to others. The study

PROTOCOL TITLE: Journaling and Addiction Recovery

VERSION DATE: 13 April 2021

will provide lap desks for participants to use to lean on when writing their journal entries unless we use a room with a table to lean on (this is not relevant to electronic administration). One additional journal will be provided if the original journal is lost or stolen during the group sessions.

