"We will not ask you about child or vulnerable adult abuse. If you tell us about child or vulnerable adult abuse or neglect, we may have to report it to authorities because of law or policy. This is true if you tell us in group, one on one meetings, or in journal entries. Also, if we learn (in person or in any other contact you have with us) that you are at risk for hurting yourself or others, we will inform NUWAY treatment staff of this information as soon as possible.

"In general, if something worries us about what you share with us in any way, we will let NUWAY staff know. This includes any time you tell us that you have used drugs or alcohol. Telling us that you have used drugs or alcohol will have the same consequences as if you told a NUWAY staff member that you used drugs or alcohol. NUWAY staff would work with you to make sure that you have the support you need to get back on track related to your recovery.

"If you tell us that you committed a crime, we would tell NUWAY Staff. Telling us that you committed a crime would have the same consequences as if you told a NUWAY staff member that you committed a crime. If you are on probation or parole, NUWAY staff would need to report this to your probation or parole officer.

"If you tell us that you intend to hurt yourself or someone else, we would tell NUWAY staff.

"Some of these things that you might tell us might have consequences related to your treatment status at NUWAY.

"In general, the NUWAY Staff will not find out your answers to the iPad surveys."

11. Number of Participants

11.1. Number of participants to be consented will be approximately 100.

12. Recruitment Methods

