Aside from signing the consent forms, and the “codename” form, The participants’ name will be retained in REDCap but all other data (from the Qualtrics surveys for example) will be separated from the participant’s name; only research staff will have access to a document(s) that links participant number/codename and name. All of the information obtained from subjects is entirely for research purposes and quoted by codename or number and kept in locked confidential files at our offices at the University of Minnesota or on password protected laptops or university servers. This information is not available to anyone except the investigators.

Although our sample participants will have been in treatment a minimum of 2 weeks and no longer suffering from the acute physical withdrawal effects of alcohol or drug abstinence, continued abstinence from drugs and alcohol is often associated with irritability, restlessness, anxiety, depressed mood, sleep disturbance, increased appetite, and decreased concentration. Abstinence also may exacerbate pre-existing conditions. Although these symptoms may be effectively treated with appropriate intervention, we will monitor these symptoms at each session. Individuals reporting moderate or persistent concerns or problems will be referred by study staff to appropriate medical/psychiatric staff at NUWAY. We will periodically

evaluate the data collected regarding both harms and benefits to determine whether participants remain safe.

Study Research Assistants or PI [name] will review the data, especially the pictures of the journal entries, as soon as possible after submission but no later than 72 hours after submission to examine the data for any safety concerns.

If participants experience distress related to the baseline questionnaire, including the question that asks about history of trauma, we will refer them to NUWAY staff.

We will use the Zoom waiting room feature and we will only admit group members into the Zoom room. If a group member behaves inappropriately (e.g., shares inappropriate words or images, i.e., Zoom bombing) we will remove them from the Zoom room.

20. Provisions to Protect the Privacy Interests of Participants

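### Use told to study staff is passed into the NUWAY record that supplies the recurrence outcome, and only the PPJ arm has groups and journals in which to tell it, so ascertainment is unequal by arm

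*Combined protocol and SAP*

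**What the plan says.** **Outcome and source.** Section 3.1 lists rates of substance use among the primary outcomes. Section 5.2 (after the outcome measures) states: "Recurrence of substance use and treatment retention will be assessed via NUWAY treatment record". It continues: "Recurrence of substance use is assessed at NUWAY by positive urine analyses (UAs) and other drug screens as well as resident self-report". Section 20.2 reads as if any one source is enough: "Resumption of substance use is confirmed at NUWAY via urine testing or other drug screening or client self-report". Section 5.4 is narrower. There, study staff ask NUWAY only whether the person has had a positive urine screen.

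**Disclosure rule.** Section 10.2 quotes consent language under which worrying information goes to NUWAY: "This includes any time you tell us that you have used drugs or alcohol". It adds: "Telling us that you have used drugs or alcohol will have the same consequences as if you told a NUWAY staff member". For survey answers the rule differs: "In general, the NUWAY Staff will not find out your answers to the iPad surveys".

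**Contact by arm.** In the PPJ arm, section 5.2 plans 8 hours of group sessions in which journal content, including bad things that happened, is shared. On attendance it says: "A NUWAY Inc. staff member will sit in on all group sessions". Section 14.1 makes that attendance optional and less needed in remote delivery. PPJ participants also upload photographs of journal pages. Under section 19.2, study staff review submitted data for safety concerns, "especially the pictures of the journal entries, as soon as possible after submission but no later than 72 hours after submission". Over the same weeks controls complete Qualtrics surveys only.

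**Contact common to both arms.** Both arms have an exit interview at about five weeks and a follow-up interview about 30 days later. The follow-up interview asks about use since the previous meeting or over the past 30 days.

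**The concern.** A randomised comparison of an event rate needs the same chance of recording the event in each arm. Here the study adds a route into the record: a participant mentions use to study staff, staff tell NUWAY, and NUWAY may log it as self-reported use. For the five weeks of group and independent practice, that route is much wider in the PPJ arm. Two participants with the same lapse could then be recorded differently because of their allocation.

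Extra capture in the PPJ arm would make PPJ look worse on recurrence or hide a benefit. Table 2 tallies recurrence after Phase 1 and after Phase 2, which is the period when the routes differ. The Analysis Plan also compares study rates with NUWAY's general rates, and NUWAY's other clients have no study route at all. Section 17.3 uses the pilot's descriptive statistics to size a larger trial, so a distorted recurrence rate would carry forward. The plan does not record how a recurrence came to light and does not mention unequal ascertainment.

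**Working it through.** **1. The plan's own figure.** Section 17.2 gives abstinence of 41.5% v 24.8% with N=76. Assuming 38 per arm and the arcsine effect size, h = 2·asin(√0.415) − 2·asin(√0.248) = 0.357, and h·√(38/2) = 1.558.
- One-sided 0.10: Φ(1.558 − 1.282) = 0.61.
- Two-sided 0.05: Φ(1.558 − 1.960) = 0.34.

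Both stated figures reproduce. They take detection to be complete and equal in both arms.

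**2. False difference when there is no true effect.** Let p be true recurrence (the same in both arms), s the share NUWAY detects by its own routes, and c the share of the remainder that reaches NUWAY only through PPJ contact. Then

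false difference = p(1 − s)c.

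Input p = 1 − 0.733 = 0.267 comes from Relevant Study #3 in section 2.2: 15 women, one arm, a different and residential site. Inputs s and c are assumptions, because the documents give no detection rates.

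| s | c | False excess in PPJ | People, if 50 per arm |
|---|---|---|---|
| 0.8 | 0.1 | 0.267×0.2×0.1 = 0.5 points | 0.3 |
| 0.6 | 0.3 | 0.267×0.4×0.3 = 3.2 points | 1.6 |
| 0.5 | 0.5 | 0.267×0.5×0.5 = 6.7 points | 3.3 |

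The figure scales with p. With p = 0.585 (one minus the 41.5% in 17.2) the same rows give 1.2, 7.0 and 14.6 points.

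**3. Effect on a true difference.** Take true recurrence of 58.5% PPJ v 75.2% control (17.2, a 16.7-point difference) and multiply by assumed detection.
- 70% in both arms: 52.6% v 41.0%, leaving 11.7 points.
- 70% control, 80% PPJ: 52.6% v 46.8%, leaving 5.8 points.
- 80% control, 90% PPJ: 60.2% v 52.7%, leaving 7.5 points.
- 70% control, 90% PPJ: no difference left. This needs c = 2/3, above the range in step 2.

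**4. Would deleting study-originated events cure it?** Suppose disclosure to the study is independent of NUWAY detection and comes first when both occur. Deletion then also removes PPJ cases NUWAY would have found itself. With s = 0.6 and c = 0.3, PPJ counts 0.267×0.6×0.7 = 11.2% against 0.267×0.6 = 16.0% in controls. That is 4.8 points in PPJ's favour, more than the 3.2 points being corrected.

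**The case against.** The strongest reply is that the text shows unequal opportunity, not unequal detection. Consent warns both arms that disclosed use has consequences, which could make PPJ participants withhold. Section 12.2 lets participants miss NUWAY groups to attend PPJ groups, which removes some ordinary opportunity to disclose. Usual care at the two outpatient sites is 4 hours a day on weekdays, so 8 PPJ hours sit beside roughly 50 to 60 hours of treatment over 2.5 to 3 weeks, as well as drug testing. These points stand as limits on direction and size. They do not make the routes equal.

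Section 5.4 is a real obstacle. If only positive urine screens count, a disclosure is not itself an event and could act only by prompting a test. Sections 5.2 and 20.2 say otherwise, so the passages must be reconciled.

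The journal route is thinner than the group route. Section 14.1 names self-harm, harm to others and abuse as what entries are monitored for, not use, and participants are advised to write in codes. The link for journals rests on the broad rule in 10.2 and the safety review in 19.2. The group route does not depend on it.

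Symmetric measurement exists in part. Both arms are asked about use at the 30-day interview, but its recall period starts at about the exit interview and so misses the five-week window. The protocol text does not list use as an exit-interview topic, and the script is not among the documents. Table 2's column heading allows recurrence to be asked or tallied, and 14.1 mentions in passing that questionnaires ask about substance use. The measures list nevertheless contains no recent-use item, and 5.2 names the NUWAY record as the source.

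That the trial is an underpowered pilot limits the consequence but does not remove it, since its rates feed the next design.

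**Conclusion.** The plan as written ascertains a primary outcome unequally by arm during the five-week study period. This follows from the text, provided self-report counts as 5.2 and 20.2 say. The likely direction is against PPJ, but that is an inference. If true recurrence is 26.7% in both arms, the false difference is about 0.5 to 7 points over the assumed detection rates. It is trivial at the low end and grows in proportion to true recurrence. It is worth correcting because the correction is cheap.

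Four stronger readings are tempting and not supported.
- *The bias is a stated share of the planned effect.* Setting 6.7 points, built on 26.7% recurrence in 15 women at another site, against the 16.7-point difference in 17.2 mixes populations with very different recurrence.
- *PPJ recurrence will be over-detected.* The documents show opportunity only and give no detection rates.
- *Retention is biased too.* Section 10.2 says some disclosures may affect treatment status, but that sentence also covers crimes and intent to harm, and its specific response to use is support. An effect is possible, not shown.
- *The source can never be recovered later.* No passage says what NUWAY's record holds on source. The plan simply makes no provision to collect it.

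**What to change.** Leave the reporting of concerns to NUWAY unchanged, and reconcile 5.2, 5.4 and 20.2 on what counts as recurrence. Then:

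1. In REDCap, record the source and date of every recurrence: NUWAY drug test, self-report to NUWAY outside the study, or study-originated (group, journal or study interview). Flag any test ordered after a study-originated disclosure.
2. Make the main between-arm comparison one that is ascertained the same way in both arms: positive results on NUWAY's drug screening, counted whether or not a study disclosure came first. Confirm with NUWAY that screening does not depend on allocation, since the protocol does not describe its schedule. Report the all-source result and the source breakdown by arm, with a sensitivity analysis for disclosure-prompted tests. Do not simply delete study-originated events.
3. Add one identical item (any use, number of days) to the Qualtrics surveys both arms complete after Phase 1, after Phase 2 and at 1 month. Handle the answers the same way in both arms and use the item as a supporting measure.

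The cost is one REDCap field, one survey item, a short addition to the Analysis Plan and an IRB modification. The downside is that recurrences known only by self-report leave the main comparison. They remain in the all-source result.
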